6.2 Assessments

6.2.1 Efficacy

All psychometric measures (see appendix) will be evaluated at intake, discharge, follow-up. All of these measures have evidence of reliability and validity in adults in this age range and include target specific measures of NF1 have recommended in previous trials. The **primary research** question is what is the feasibility of the *iCanCope-NF* program? We define feasibility as (1) rates of accrual and dropout, daily logins, engagement, and outcome measures completed and (2) perceptions regarding intervention acceptability and satisfaction; and what are the levels of engagement. logins, with the intervention? The **secondary questions** are: (1) how does the *iCanCope-NF* program compare with the control condition in differences of pain and pain-related activity limitations, sleep functioning, emotional functioning (depression, anxiety), opioid usage, pain catastrophizing, self-efficacy, respondent burden (i.e. Physical Functioning, R, Vitality, Social Functioning, Role-Emotional, and Mental Health), and psychological flexibility immediately post-treatment (T2), (2) does the *iCanCope-NF + CM* increase the engagement of the *iCanCope-NF* program as compared to *iCanCope-NF* without CM, and do their corresponding levels of pain and pain-

related activity decrease with CM?, and (3) do individuals with NF1 utilize the MBAA to help reduce pain symptoms? We hypothesize that by customizing and including MBAA to the program for adults with NF1, that individuals who engage regularly as seen through Analytics Platform for Evaluating Effective Engagement (APEEE) application, will acquire new sets of skills to facilitate pain management, while pain as reported with the Brief Pain Inventory will decrease.

6.2.2 Safety/Pregnancy-related Procedure

N/A

6.2.3 Adverse Events Definition and Reporting

In the event your behavioral study involves a drug or device intervention consider the following sample language:

Adverse event means any untoward medical occurrence associated with the use of an intervention in humans, whether or not considered intervention related.

An adverse event (AE) or suspected adverse reaction is considered "serious" if, in the view of either the investigator or sponsor, it results in any of the following outcomes: death, a life-threatening adverse event, inpatient hospitalization or prolongation of existing hospitalization, a persistent or significant incapacity or substantial disruption of the ability to conduct normal life functions, or a congenital anomaly/birth defect. Important medical events that may not result in death, be life-threatening, or require hospitalization may be considered serious when, based upon appropriate medical judgment, they may jeopardize the participant and may require medical or surgical intervention to prevent one of the outcomes listed in this definition. Examples of such medical events include allergic bronchospasm requiring intensive treatment in an emergency room or at home, blood dyscrasias or convulsions that do not result in inpatient hospitalization, or the development of drug dependency or drug abuse.

The following guidelines will be used to describe severity of adverse events.

- Mild — Events require minimal or no treatment and do not interfere with the participant's daily activities.
- Moderate — Events result in a low level of inconvenience or concern with the therapeutic measures. Moderate events may cause some interference with functioning.
- Severe — Events interrupt a participant's usual daily activity and may require systemic drug therapy or other treatment. Severe events are usually potentially life-threatening or incapacitating. Of note, the term "severe" does not necessarily equate to "serious".

All adverse events (AEs) must have their relationship to study intervention assessed by the investigator who examines and evaluates the participant based on temporal relationship and his/her clinical judgment. The degree of certainty about causality will be graded using the categories below.

- Related — The AE is known to occur with the study intervention, there is a reasonable possibility that the study intervention caused the AE, or there is a temporal relationship between the study intervention and event. Reasonable possibility means that there is evidence to suggest a causal relationship between the study intervention and the AE.
- Not Related — There is not a reasonable possibility that the administration of the study intervention caused the event, there is no temporal relationship between the study intervention and event onset, or an alternate etiology has been established.

OR

- Definitely Related — There is clear evidence to suggest a causal relationship, and other possible contributing factors can be ruled out. The clinical event, including an abnormal laboratory test result, occurs in a plausible time relationship to study intervention administration and cannot be explained by concurrent disease or other drugs or chemicals. The response to withdrawal of the study intervention (dechallenge) should be clinically plausible. The event must be pharmacologically or phenomenologically definitive, with use of a satisfactory rechallenge procedure if necessary.
- Probably Related — There is evidence to suggest a causal relationship, and the influence of other factors is unlikely. The clinical event, including an abnormal laboratory test result, occurs within a reasonable time after administration of the study intervention, is unlikely to be attributed to concurrent disease or other drugs or chemicals, and follows a clinically reasonable response on withdrawal (dechallenge). Rechallenge information is not required to fulfill this definition.
- Potentially Related — There is some evidence to suggest a causal relationship (e.g., the event occurred within a reasonable time after administration of the trial medication). However, other factors may have contributed to the event (e.g., the participant's clinical condition, other concomitant events). Although an AE may rate only as "possibly related" soon after discovery, it can be flagged as requiring more information and later be upgraded to "probably related" or "definitely related", as appropriate.
- Unlikely to be related — A clinical event, including an abnormal laboratory test result, whose temporal relationship to study intervention administration makes a causal relationship improbable (e.g., the event did not occur within a reasonable time after administration of the study intervention) and in which other drugs or chemicals or underlying disease provides plausible explanations (e.g., the participant's clinical condition, other concomitant treatments).
- Not Related — The AE is completely independent of study intervention administration, and/or evidence exists that the event is definitely related to another etiology. There must be an alternative, definitive etiology documented by the clinician.

The PI ([name]) will be responsible for determining whether an adverse event (AE) is expected or unexpected. An AE will be considered unexpected if the nature, severity, or frequency of the event is not consistent with the risk information previously described for the study intervention.

The occurrence of an adverse event (AE) or serious adverse event (SAE) may come to the attention of study personnel during study visits and interviews of a study participant presenting for medical care, or upon review by a study monitor.

Any medical condition that is present at the time that the participant is screened will be considered as baseline and not reported as an AE. However, if the study participant's condition deteriorates at any time during the study, it will be recorded as an AE.

Changes in the severity of an AE will be documented to allow an assessment of the duration of the event at each level of severity to be performed. AEs characterized as intermittent require documentation of onset and duration of each episode.

The PI ([name]) will record all reportable events with start dates occurring any time after informed consent is obtained until 7 (for non-serious AEs) or 30 days (for SAEs) after the last day of study participation. At each study visit, the investigator will inquire about the occurrence of AE/SAEs since the last visit. Events will be followed for outcome information until resolution or stabilization.

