6.3 Study Procedures

6.3.1 Study Schedule

A total of three visits (all virtual) will be completed. The three visits will consist of admission, discharge and follow-up. Admission for control group will consist of 30 minutes, while admission for individuals within the experimental groups, should take 60 minutes. Discharge evaluations for each should be 45 minutes (30 minutes for assessments, 15 minutes debriefing). Follow-up should be 30 minutes for assessments. Individuals who have access to the mobile application are encouraged to provide daily check-in evaluations (estimated time of 2 minutes) and utilize the different modules at their discretion. The participants will have free reign of the mobile application and are not required to spend any time on the mobile application. No other communication with the research team will take place between all participants and the time intervals previously mentioned. For individuals who are placed in the control group, they will be encouraged to utilize the materials found on several chronic pain websites, with no required time commitments. The mobile application will not remind or notify the participant if they have to login or input information.

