6.3.6 End of Study and Follow Up

At the end of the study, all participants in each group (TAU, iCanCope, iCanCope+CM) will be required to complete the identical set of assessments at intake, minus demographic information. Individuals who prematurely left early or who withdrawn from the study will not be asked to complete the end of the study survey. Additionally, individuals with access to the iCanCope mobile application license will end and will not be able utilize the mobile application until the follow-up is complete. For individuals who did not have access to the iCanCope mobile application they will continue not having access to the mobile application.

All participants in each group will complete a 6-week post discharge follow-up. The follow-up will be identical to the discharge evaluation. Individuals will be emailed a secured email by the research assistant to complete the survey one day before the 6-week survey. All participants will have a one-week (7days) to complete the assessment, and a reminder email will be sent on the last day of the survey to the participants. Individuals will not be required to complete but will be encouraged to do so.

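### Adverse events are asked about only at visits, so early leavers may have no inquiry after baseline, and those who skip the optional follow-up have none after discharge

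*Combined protocol and SAP*

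**What the plan says.** Section 6.2.3 has the PI record reportable events from consent "until 7 (for non-serious AEs) or 30 days (for SAEs) after the last day of study participation". The plan does not define that last day.

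For active ascertainment the same section says: "At each study visit, the investigator will inquire about the occurrence of AE/SAEs since the last visit". It also names passive routes: a participant presenting for medical care, or review by a monitor. For events already known, "Events will be followed for outcome information until resolution or stabilization".

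Section 6.3.1 sets the calendar, all of it virtual: "The three visits will consist of admission, discharge and follow-up". It adds: "No other communication with the research team will take place between all participants and the time intervals previously mentioned". That sentence is garbled and may refer only to the time between visits.

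Section 6.3.6 narrows who is reached. On early leavers: "Individuals who prematurely left early or who withdrawn from the study will not be asked to complete the end of the study survey". The follow-up, six weeks after discharge, is an online survey sent by email: "Individuals will be emailed a secured email by the research assistant to complete the survey one day before the 6-week survey". Participants have seven days to answer. On whether they must: "Individuals will not be required to complete but will be encouraged to do so".

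**The concern.** The window is fixed by days after the end of participation, while asking is fixed to visits. Two groups can miss the visits. Early leavers are excused from the discharge survey, and no other inquiry is described for them. People who finish treatment but do not return the follow-up survey are last asked at discharge.

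In both groups a new event enters the record only if it happens to reach the team. The study is remote and recruits through national advocacy networks, so a visit to a local emergency department has no described path to the investigator. Section 6.3.7 foresees withdrawal for psychological deterioration, so some of those who leave may be the people one would most want to ask. An absence of reports from these groups could not be read as an absence of events.

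The undefined last day adds uncertainty. Sections 6.1.1 (control group) and 6.3.6 use end-of-study language for discharge. Section 6.3.1 counts follow-up as a study visit, and section 5.2.1 puts study completion at four months on average. Two staff members could disagree on whether a hospitalization on day 100 must be recorded.

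**Working it through.** The plan gives no figure here to reproduce. The check sets the visit calendar against the recording window.

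**Inputs**
- Treatment lasts 8 weeks (6.1.1), so discharge falls on day 8 × 7 = 56, taking consent and admission as day 0 (assumption).
- Follow-up is 6 weeks after discharge (6.3.6): day 56 + 42 = 98.
- Recording continues 7 days (AE) or 30 days (SAE) after the last day of participation (6.2.3).
- Each inquiry looks back to the previous visit (6.2.3).

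**Formula.** Window length = last day + 7 or + 30. Days with no planned inquiry = window end − day of the last inquiry, or 0 if an inquiry falls after the window closes.

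**Participant who completes discharge but skips follow-up (last inquiry on day 56)**

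| Last day taken as | SAE window | SAE days not asked about | AE window | AE days not asked about |
|---|---|---|---|---|
| Discharge, day 56 | 56 + 30 = 86 | 86 − 56 = 30 (30/86 = 35%) | 56 + 7 = 63 | 63 − 56 = 7 (7/63 = 11%) |
| Follow-up, day 98 | 98 + 30 = 128 | 128 − 56 = 72 (72/128 = 56%) | 98 + 7 = 105 | 105 − 56 = 49 (49/105 = 47%) |

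**Participant who completes follow-up.** If the last day is discharge, the day-98 inquiry looks back over both windows and nothing is missed (0/86 and 0/63). If the last day is follow-up, tails of 30/128 days (23%) for SAEs and 7/105 days (7%) for AEs rest on spontaneous reports.

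**Early leaver.** Someone leaving on day L, before day 56, has an SAE window of L + 30 days. For L = 28 (an illustrative date) the SAE window ends on day 58 and the AE window on day 35. If no AE question is put at exit, the last inquiry is admission and the whole window goes unasked. That follows from the condition and measures nothing. What matters is whether an exit question exists, and the visible text describes none.

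**Numbers affected.** Section 6.4.2 gives 20% attrition but not its timing, and no follow-up return rate is given. No count of participants or missed events can be derived.

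**The case against.** The strongest reply is that the early-leaver gap is inferred from silence. Section 6.3.6 waives a survey, whereas section 6.2.3 gives the AE inquiry to the investigator at a visit. Section 6.3.1 allots discharge 15 minutes of debriefing besides the assessments, so survey and visit are not the same thing. Nothing forbids an AE question at withdrawal, and section 6.3.7 has staff helping participants withdrawn for deterioration. Section 6.3.5 points to Appendix 3 and section 7.6 to a standard operating procedure, neither of which is visible. This stands. A reader might infer that early leavers are certainly never asked, but the documents support only that they may not be.

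A reader might also infer that any window running past the last visit contradicts the visit schedule. It does not. Passive reporting after a completer's final visit is ordinary practice, so the completer tails above are not part of the point.

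Three further limits are fair. Section 6.2.3 opens with uncompleted template wording, which may explain the mismatch, though the commitment remains in the text. The window applies to reportable events, which section 7.12 defines narrowly (serious or life-threatening, unanticipated or more frequent than expected, and at least possibly related). That fits poorly with a 7-day window for non-serious AEs, but it reduces what would be recorded. Finally, the PI reviews safety monthly (7.12) or at least quarterly (7.11). Such review can examine only what has been reported.

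The follow-up part does not depend on silence in the same way: inquiry at visits and an optional last visit are both stated rules.

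**Conclusion.** The point holds as a modest gap in safety ascertainment. Under the stated rules, a participant who skips follow-up has no planned inquiry for 35% of the SAE window if participation ends at discharge, or 56% if it ends at follow-up. Early leavers may have none after baseline. The percentages assume admission on day 0 and discharge and follow-up on their nominal days. The early-leaver part also assumes that no exit inquiry is described in the appendices.

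A reader might take this for a major safety failure or a threat to the trial's results. The documents support neither. Section 7.12 rates the study as minimal risk, app access ends at discharge, known events are followed up, and no planned outcome or analysis uses AE data. The lack of a definition for the last day would, alone, be only a missing detail. It matters here because it moves the end of the SAE window from day 86 to day 128. The change is worth making because it is cheap.

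**What to change.** 1. Put a short AE/SAE item (new or worse health problem, hospital or emergency visit, date) in the discharge and follow-up Qualtrics surveys in all three arms, with positive answers passed to the investigator.
2. Ask the same item at withdrawal.
3. About 30 days after the last day of participation, send one automated email with that item to early leavers and follow-up non-returners who have not refused contact.
4. Define the last day as the date the follow-up survey is returned, the close of its 7-day response period if it is not returned, or the withdrawal date for early leavers.
5. Amend sections 6.3.1 and 6.3.6 so that these contacts are allowed.

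The cost is one definition, one survey block and one email, using a survey platform already in place, plus an IRB amendment. There will be a few more reports to review, and response to the closing email will be incomplete, so the gap will shrink but not vanish.

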6.2.4 Pharmacokinetics (if applicable)

N/A

6.2.5 Biomarkers (if applicable)

N/A

6.3 Study Procedures

6.3.1 Study Schedule

A total of three visits (all virtual) will be completed. The three visits will consist of admission, discharge and follow-up. Admission for control group will consist of 30 minutes, while admission for individuals within the experimental groups, should take 60 minutes. Discharge evaluations for each should be 45 minutes (30 minutes for assessments, 15 minutes debriefing). Follow-up should be 30 minutes for assessments. Individuals who have access to the mobile application are encouraged to provide daily check-in evaluations (estimated time of 2 minutes) and utilize the different modules at their discretion. The participants will have free reign of the mobile application and are not required to spend any time on the mobile application. No other communication with the research team will take place between all participants and the time intervals previously mentioned. For individuals who are placed in the control group, they will be encouraged to utilize the materials found on several chronic pain websites, with no required time commitments. The mobile application will not remind or notify the participant if they have to login or input information.

6.3.2 Informed Consent

A waiver of documentation of consent will be requested considering that the entire research study is performed remotely. The consent will describe in detail the study intervention, study procedures, and risks are given to the participant. The consent will be uploaded through the initial meeting between the research team and the participant. Consent is required prior to starting study procedures/administering study intervention. The following consent materials are submitted with this protocol Phase 3 consent form.

6.3.3 Screening

Subjects will be interviewed by a trained and supervised research assistant to determine interest in participating in the study and eligibility. Participants will be interviewed via Zoom using standardized psychological assessments or will complete similar standardized self-report forms. Eligibility will be evaluated by the research assistant and reviewed with the project director or PI prior to initiation

6.3.4 Recruitment, Enrollment and Retention

Describe how potential subjects will be identified:

Adults with NF1 will be recruited from advocacy groups: NF Network and NF Northeast. NF Network and NF Northeast are the largest direct support and advocacy cohorts for individuals and families with neurofibromatosis in the United States. NF Network has over 28,000 members on their private network, while NF Northeast has over 2,500 individuals on their private network.

Describe how potential subjects are contacted:

Each advocacy group has granted permission for us to contact individuals through their websites via email and private Facebook banners. Examples of the emails are attached (see Recruitment Emails).

Who is recruiting potential subjects?

The Principal Investigator (PI; [name]) or his research assistant will be responsible for all recruitment of individuals with NF1.

How will this process take place, including obtaining consent in relation to the start of the study procedures?

Individuals with NF1 are consented through the Zoom (www.zoom.com (<http://www.zoom.com>); A Yale-approved vendor). The consent form will be an attached document, that can be shared with them while the PI ([name])/RA reads the consent form. Zoom allows the PI/RA to interact with the individual with NF1 or the clinician to ensure any and all questions are answered prior to the participation of the study.

Use of third parties: N/A

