2.1 Background

Background: Neurofibromatosis Type 1 (NF1) is an autosomal dominant genetic condition affecting 1 in 2500 individuals (1). NF1 was originally classified as a tumor predisposition

syndrome based on the propensity of affected children and adults to develop benign and malignant tumors (2,3). Over 50% of individuals with NF1 report significant pain and discomfort (4,5) which can be associated with tumors, but is often not localized to a structural lesion, thus presenting treatment challenges for patients and their medical caregivers. Moreover, the increased pain in this population can negatively impact an individual's perceived quality of life (6,7). Due to the complexity of the disorder (e.g., location, severity, number, and type of tumors), there are limited effective therapeutic options for treating pain (3). In this regard, tumor-related pain is primarily managed by either surgery or medication (8,9). To date, there has been limited research exploring the daily impact of living with persistent pain from a qualitative perspective by the individual living with NF1 and evaluating NF1 pain and treatments.

Barriers to Pain Treatment: Individuals suffering from persistent pain have multiple potential barriers to obtaining comprehensive pain specific treatment including: (a) difficulty accessing these services (e.g., no services available in many geographic areas, long wait times); (b) limited availability of trained professionals such as psychologists, particularly in non-urban centers; (c) patient-related issues (i.e., psychological, communication, and attitude); (d) current health care system barriers, (i.e., reimbursement, costs of treatment) and (e) limited access to self-management techniques (10-14). Self-management can be defined as the individual's ability to manage the symptoms, treatment, physical, and psychological consequences and lifestyle changes inherent to living with a chronic illness (15). Self-management interventions that provide individuals with disease-specific knowledge, strategies to manage symptoms such as pain (e.g., cognitive-behavioral therapies; CBT), and social support are needed to promote optimal health outcomes.

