5.3.2 Eligibility Criteria/Vulnerable Populations

Patients will be included in the study if they meet the following inclusion criteria:

- 1) adults older than age of 18
- 2) diagnosis a diagnosis of NF1;
- 3) permanently reside in the United States and
- 4) have pain interference aggregate scores of three or more in the last two weeks using the Brief Pain Inventory-Short Form (BPI-SF) scale.

Patients will be excluded if they: 1) have an undiagnosed case of NF1; 2) have documented major co-occurring psychiatric disease; 3) have moderate to severe cognitive deficits; or 4) have depression assessed using the Patient Health Questionnaire (PHQ-9) or anxiety assessed using the Generalized Anxiety Disorder scale (GAD-7) greater than or equal to the appropriate thresholds (10=mild major depression; 5=mild severe anxiety).

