6.1 Intervention

6.1.1 Description of Intervention

Figure 1 presents a CONSORT study flow diagram. Potential participants will be required to access an online secure site to learn about the study and to be evaluated for eligibility, provide informed consent, and complete baseline assessments. Eligible participants will be randomly assigned to one of the 3 conditions: *iCanCope-NF*, *iCanCope-NF +CM*, or the Control Group (treatment as usual or TAU). Individuals in the *iCanCope* groups will receive 8 weeks of 24-hour access to the program.

The proposed architecture of the *iCanCope-NF* consists of four theory-based components, integrated across smartphone: self-monitoring (e.g. Real-time symptom tracking via patient self-report. Customizable graphs and reports; smart goal setting (e.g. Set

goals related to improving pain, sleep, mood, physical activity and social activity, Adherence to SMART' framework); personalized self-management instruction and rehearsal (e.g. (In-the-moment access to pain coping strategies, Personalized instruction based on goals); and detailed pain education (Provide information on types of pain, strategies for maintaining physical activity and strategies managing anxiety, stress and emotions).

iCanCope Orientation. At study intake, individuals within the *iCanCope-NF* and *iCanCope-NF* +Contingency Management (CM) groups will receive a 10-minute video orientation to the iCanCope program. The orientation will emphasize daily usage of the CBT treatment platform. Individuals will receive a login and password information, general information and instruction, and contact information for technical problems.

iCanCope-NF Group: In this group, individuals will receive the *iCanCope-NF program*. The intervention will be delivered on a restricted password-protected mobile application.

Participants will be encouraged to log onto the pain diary app (via automated alerts) once per day over the 8-week period to complete pain diary entries and develop and track their goals related to their pain, physical, social activities, sleep, as well as work through content based on their goals.

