iCanCope-NF & CM Group: In addition to the *iCanCope-NF* activities outlined above, individuals will be rewarded with incentives such as points that are redeemable for prize-based gift card vouchers.[i] (#_edn1) Points will be accrued through access to new sections, daily check-ins, and engagement of the mobile application. Based on research, the total amount of money that can be earned by the patient over the course of the two months is 50 dollars USD. Individuals who are only randomized in the ICC-CM condition earn from \$1 to \$5 dollar amazon gift card per week for eight weeks (based on their usage). With an additional \$10 dollar gift card, if they check in every day. The total of the incentives can reach up to 50 dollars.

Control Group: The control group is designed to assess for potential effects on outcomes of time, attention, during the study. In addition to usual care, participants will be required to complete baseline and follow-up assessments similar to that of the intervention groups. They will be given that patient education, through preapproved flyers and information found from national websites regarding pain management, but no self-management strategies or opportunities for social support. They will not have access to the mobile application during the course of experiment; however, the control group will be offered the full *iCanCope-NF* program following the trial (T2) for a period of 2 months after the study is over.

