6.1.2 Method of Assignment/Randomization

Participants will be randomized to one of the three conditions using an urn randomization algorithm which modifies ongoing randomization probabilities based on prior group composition groups, and controls for other predictive factors. This process greatly reduces experimenter bias and other internal validity threats to integrity. Gender be the only variable

that will be attempted to controlled for to ensure equal representation across the groups within the urn randomization using stratification.

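### Adults from one household can be randomised to different arms, so a control could pick up coping content from a relative who has the app; a small, unquantified dilution that one eligibility line would prevent

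*Combined protocol and SAP*

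**What the plan says.** - **Inheritance.** Section 2.1: "Neurofibromatosis Type 1 (NF1) is an autosomal dominant genetic condition affecting 1 in 2500 individuals". More than one affected adult in a family is therefore plausible.
- **Recruitment.** Section 6.3.4 recruits by email and private Facebook banners through two networks: "NF Network and NF Northeast are the largest direct support and advocacy cohorts for individuals and families with neurofibromatosis in the United States".
- **Eligibility.** Neither list in section 5.3.2 mentions a relative or household member who is already enrolled. Sections 5.3 and 5.3.2 give no upper age limit; the synopsis and section 5.3.1 give 18-34.
- **Allocation.** Section 6.1.2: "Participants will be randomized to one of the three conditions using an urn randomization algorithm". The unit is the person, and the only balancing factor is gender ("Gender be the only variable").
- **Control condition.** Section 6.1.1 says of controls: "They will not have access to the mobile application during the course of experiment". They receive educational flyers and website information on pain, but are not to be taught self-management or offered social support.
- **Access to the app.** Section 6.1.1: "The intervention will be delivered on a restricted password-protected mobile application". Section 3.3.1 adds a personal identifier and passcode.
- **Analysis.** Section 6.4.3.1 allows for serial correlation within a participant. The estimating-equation and multilevel models in section 6.4.3.2 define no cluster, and section 6.4.4 (subsets and covariates) is marked not applicable. Nothing in the documents addresses enrolled relatives, shared households or contamination between arms.

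**The concern.** One recruitment message can reach several affected members of a family, and nothing prevents two of them from enrolling and being assigned to different arms. The app teaches symptom tracking, goal setting, coping strategies and pain education (section 6.1.1). Those are skills and information, and they can pass between people who live together by conversation or over a shared screen.

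A control who picks them up is no longer receiving the intended control condition. At stake is the comparison of app with control on pain and related outcomes at T2, which sections 6.2.1 and 6.4.3.2 pose as a secondary question. Spill-over pulls that difference towards zero, in a pilot with 36 per group whose results are meant to inform a definitive trial (section 3.2).

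**Working it through.** The plan gives no figure for related participants, so there is none to reproduce on this point.

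**Inputs from the documents.** Three arms, 36 per group, 108 in total (section 6.4.2). Equal allocation is inferred from the equal group sizes.

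**Inputs assumed.** The fraction *f* of participants in co-resident enrolled pairs; the share *s* of the app's benefit that reaches a control living with an app user (one half, or all); the intra-family correlation (ICC), 0.3-0.5.

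**1. How a pair is split (independent 1:1:1 allocation)**
- Different arms: 1 − 3 × (1/9) = 2/3.
- One in either app arm, one in control: 2 × (1/3) × (2/3) = 4/9 = 44%.
- With group sizes fixed at 36, the second figure is 2 × (36/108) × (72/107) = 0.449, so the approximation is adequate. These probabilities apply only if a pair exists; they do not say how often one does.

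**2. From pairs to dilution**

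Pairs = 108 × *f* / 2. Split pairs = pairs × 4/9. Share of controls exposed = split pairs / 36 = (2/3) × *f*. Dilution = (2/3) × *f* × *s*.

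| *f* | Pairs in 108 | Split app/control | Controls exposed | Dilution at *s* = 0.5 |
|---|---|---|---|---|
| 5% | 2.7 | 1.2 | 3.3% | 1.7% |
| 7.5% | 4.05 | 1.8 | 5.0% | 2.5% |
| 10% | 5.4 | 2.4 | 6.7% | 3.3% |
| 20% | 10.8 | 4.8 | 13.3% | 6.7% |
| 22.5% | 12.15 | 5.4 | 15.0% | 7.5% |

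Required sample size varies as 1/effect², so a 2.5% dilution is like losing 1 − 0.975² = 4.9% of the sample, and a 7.5% dilution is like losing 1 − 0.925² = 14.4%.

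**3. Effect on power**

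The plan states no effect size, SD or power. Assuming two-sided 0.05 and 80% power, 36 per group detects d = (1.960 + 0.842) × √(2/36) = 0.66. A simulation (8,000 runs per setting, ICC 0.3, t-test of one app arm against control that ignores pairing) gave:

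| *f* | Half the effect passed on | Full effect passed on |
|---|---|---|
| 0 | 79% | 79% |
| 10% | 76% | 74% |
| 20% | 73% | 65% |

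**4. Type I error**

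For one app arm against control, a pair lies wholly within one of the two arms with probability 1/9 + 1/9 = 2/9, and is split between them with probability 2 × (1/9) = 2/9. Shared family variance widens the difference in the first case and narrows it in the second, so under separate randomisation the two offset on average. The simulation agrees: the rejection rate was 0.044-0.049 with 10-40% of participants in pairs and ICC 0.3-0.5. It rose to 0.052-0.068 only when relatives were placed in the same arm and the analysis ignored this.

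**The case against.** The case on the other side is substantial.

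- **Exposure is possible, not documented.** Access is by personal login, and the app works through personal goals and tailored instruction. No passage supports a control gaining half the benefit second-hand. This stands as a limit on size. It does not remove the gap, because a passcode does not stop one person telling another what they have learned.
- **Pairs may be rare.** The networks serve individuals as well as families, and no passage describes recruiting relatives together. Both relatives would have to meet the pain criterion and pass the depression, anxiety and cognitive exclusions. Under the 18-34 range parent-child pairs are nearly ruled out, though siblings remain; with no upper age limit they are not. The top of the range above needs about 12 co-resident pairs among 108, which is a strong premise.
- **The affected comparison is narrow.** Section 6.2.1 makes feasibility the primary question. In section 5.2.1 engagement compares the two app groups, and the pain outcomes are changes within groups, so contaminated controls do not dilute the change seen in an app arm. This stands: the dilution falls on the secondary app-versus-control contrast.

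A reader might also infer that relatives in the sample break independence and so invalidate the tests. The outcomes of relatives may indeed be correlated, but the plan randomises them separately, and step 4 shows that this does not raise the false-positive rate. A reader might further infer that an app-only participant's engagement would change on learning that a relative is paid. Section 6.3.2 has the consent describe the intervention in detail, so participants may know of the incentives already, and the documents do not support a separate harm.

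**Conclusion.** The gap is real and minor. The plan allows a control to live with someone in an app arm, and neither eligibility, allocation nor analysis deals with it. The consequence is dilution of the app-versus-control difference in pain: about 2.5-7.5% if 7.5-22.5% of participants (about 4 to 12 pairs of 108) are in co-resident pairs and exposed controls gain half the benefit. Both inputs are assumptions, and with fewer pairs or less sharing the effect is smaller.

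The documents do not support the stronger statements that controls will be exposed to the app, that type I error is inflated, or that the outcomes listed as primary in section 5.2.1 are biased by this route.

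**What to change.** Add to section 5.3.2 a criterion of one participant per household, and add a question about it to the screening in section 6.3.3, before randomisation. This removes same-household spill-over by design and needs no change to the analysis.

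The cost is one criterion, one question and a few volunteers turned away. Section 5.1.1 puts the pool at about 5,000, but that estimate allows only for age and the other criteria will reduce it. Relatives living apart are not covered; recording family links at the same screening would at least show how many there are.

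The alternative of randomising households as units turns nobody away, but it needs a family term in the models and a slightly larger sample. With design effect 1 + *f* × ICC, *f* = 10-20% and ICC 0.3-0.5 give 1.03-1.10, or 38-40 per group instead of 36. Adding a family term while still randomising relatives separately would not help, because it does not restore a diluted contrast.
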